9.7.3 Statistical Methods

This descriptive study will analyze collected data to report frequencies of MenACWY-CRM exposure and analysis of medical events. The frequencies will be presented as absolute numbers and percentages of relevant total.

Frequency of exposure to MenACWY-CRM vaccination

This descriptive study will report the frequency of exposure among infants and toddlers 2-23 months of age vaccinated at least one dose of MenACWY-CRM during the study period. Frequency of exposure will be summarized as follows:

- Overall
- 1 dose
- 2 doses
- 3 doses
- 4 doses

Analysis of medical events

Eligible medical events in the study will be described as follows:

- Frequency of individual medical events

The frequency of medical events is defined as the total number of each individual event. The frequency will be described by absolute number of each individual medical event and percentage of each individual medical event of total number of captured medical events during the observation period.

If the number of medical events allows, captured medical events will be stratified by dose.

- Rate of medical events

The rate of medical events is defined as the number of all captured events divided by the total person-time following MenACWY-CRM doses administered during the study period. 95% confidence interval of the rate of medical events will be calculated. Person-time for each dose will begin at the vaccination and end at 6 months following vaccination, disenrollment, death, the end of data collection, or receipt of an additional dose of MenACWY-CRM, whichever comes first. If data permit, rate will be further stratified by dose.

▫ Description of medical events

Medical events following MenACWY-CRM exposure in children 2-23 months of age will be described. Medical events will be reviewed and described, at least including age at vaccination, gender, vaccination history, diagnoses, and if available, underlying condition. Recurrence of the same medical event after repeated MenACWY-CRM vaccination of the same person will be included in the description as well.

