5. ANALYSES OF OBJECTIVE

The outcome data will be provided for the entire population and for the following stratum if sufficient numbers are available ($n \geq 5$ in each stratum):

- Number of MenACWY-CRM doses received during the study period.

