5.1 Identification and review of events

Medical events occurring in ED and inpatient settings within 6 months following a MenACWY-CRM vaccination will be searched in the EMR.

Medical events will be characterized two ways: by encounter (hospitalization only, ED only, or both ED and hospitalization) and by diagnosis (see Appendix A, Table Shell 4 for details). The analysis allows for any recurrent events (i.e. different episodes of the same diagnosis) to be counted independently.

For characterization by encounter (Table 4a), all dates used for analysis will be the date of the ED encounter or hospital admission. Encounters will be considered pre-existing if all diagnoses made during the encounter are present in the medical record prior to the first dose of vaccine. Upon chart review by the study physician co-investigator, an encounter will be refuted if it is found to not be a true ED or hospital encounter. Each encounter will be reported as a single event, regardless of the number of diagnoses made during the encounter.

For characterization by diagnosis (Table 4b), all dates used for analysis will be the first date that the diagnosis is recorded in the EMR in any medical setting. A diagnosis will be excluded as pre-existing if the same ICD diagnosis code appears in any medical setting prior to the first dose of MenACWY-CRM vaccination. A diagnosis will be considered refuted if, upon chart review by the study physician co-investigator, there is no evidence of the diagnosis in the medical record. Multiple diagnoses associated with the same episode will be identified, but only the first diagnosis date (in any setting) will be counted in the analysis of each episode. Subsequent diagnoses for the same episode will be marked in Table 4b as “Diagnosis is continuation of an ongoing episode.” An episode will be considered as ended when there is symptom resolution as determined by chart review (e.g., symptoms stated to have resolved or the diagnosis/symptoms have been absent from the medical record before they are mentioned again). In the case of recurrent events, the date used will be the date of the first diagnosis in the medical record following resolution of the prior episode. Recurrent events will be marked in Table 4b as “Diagnosis is a recurrence”. Each diagnosis will be described independently. It is possible that different diagnoses from the same inpatient or ED encounter could have different diagnosis

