5.2 Frequency and rate of events

The frequency of medical events is defined as the total number of each individual event. The frequency will be described by absolute number of each individual medical event and percentage of each individual medical event out of the total number of captured medical events during the observation period and included for analysis (as per Tables 4a or 4b).

The rate of medical events is defined as the number of all captured events divided by the total person-time following MenACWY-CRM doses administered during the study period. The rate and Poisson 95% confidence interval of the rate of medical events will be calculated and presented as number per 1000 person-years using SAS PROC GENMOD.

If the number of medical events allows, captured medical events will be stratified by dose and by the status of the diagnosis as first occurrence or recurrence. Person-time for each dose will begin at the date of vaccination and end at 6 months following vaccination, disenrollment, death, the end of data collection, or receipt of an additional dose of MenACWY-CRM, whichever comes first.

Frequency and rate of events will be characterized two ways: by encounter (hospitalization only, ED only, or both ED and hospitalization) and by diagnosis (see Appendix A, Table Shell 5 for details). For the analysis by encounter, the encounter date will be used to determine the timing of the encounter relative to the timing of vaccine dose. For the analysis by diagnosis, the first diagnosis date for each diagnosis in any care setting will be used to determine the timing of the diagnosis relative to the timing of vaccine dose. The analysis by diagnosis will be stratified by setting of diagnosis and recurrence when the number of events in each stratum is ≥ 5 . The setting of diagnosis reflects whether the diagnosis was captured by automated search in the inpatient setting, ED setting, or both. If possible, diagnoses will be grouped by category, and the frequency and rate of diagnoses will be presented by category.

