8. LIST OF REPORT TABLES, LISTINGS AND FIGURES

	Population* (all or per event)	Description	Strata**
Table 1	All	Study population selection	
Table 2	All	Baseline Characteristics of MenACWY-CRM recipients 2-23 months of age	Number of vaccinations received
Table 3	All	Follow-up characteristics of MenACWY-CRM recipients 2-23 months of age	Number of vaccinations received
Table 4	Per event	Summary of event identification and review	
Table 5	Per event	Frequency and rate of events among infant MenACWY-CRM recipients	Number of vaccinations received, care setting (5b only), recurrence (5b only)
Table 6	Per event	Description of diagnoses among infant MenACWY-CRM recipients	
Figure 1	All	Vaccinations by Month	Number of vaccinations received

*All = all MenACWY-CRM recipients,

Per event will include all recipients with no history of that event prior to the first MenACWY-CRM dose

** Data are only presented in stratum if sufficient numbers are available in each stratum ($n \geq 5$).

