Number of recipients experiencing multiple different hospitalization or emergency encounters							
N/A = Not Applicable							

Table 4b: Summary of Diagnosis Identification and Review

Event	Automated Algorithm			Physician Review			Diagnosis is continuation of an ongoing episode (g)	Diagnosis is a recurrence (h)	Total Diagnoses for Analysis (i=a-b-e-f-g)
	Potential diagnoses identified (a)	Excluded diagnoses based on pre-existing condition (b)	Diagnoses remaining from automated algorithm identification (c=a-b)	Diagnoses confirmed (d)	Diagnoses refuted (e)	Confirmed events with diagnosis determined to be prior to index vaccination (f)			
Specific diagnoses									
diagnosis 1									
diagnosis 2									
Diagnosis groupings									
grouping 1									
grouping 2									
Number of recipients experiencing a single diagnosis									
Number of recipients experiencing multiple different diagnoses									

N/A = Not Applicable

Table 5a: Frequency and rate of hospitalization and emergency events observed following vaccination with MenACWY-CRM

Event	Overall		Number of vaccines received prior to event							
			One		Two		Three		Four	
	Frequency n (%)	Rate (95% CI)*	Frequency n (%)	Rate (95% CI)*	Frequency n (%)	Rate (95% CI)*	Frequency n (%)	Rate (95% CI)*	Frequency n (%)	Rate (95% CI)*
Hospitalization only										
Emergency department only										
Emergency department and hospitalization										

*Events per 1000 person years

Table 5b: Frequency and rate of diagnoses observed following vaccination with MenACWY-CRM

Event	Overall		Number of vaccines received prior to event								Setting of initial presentation with the diagnosis*						First occurrence or recurrence			
			One		Two		Three		Four		Inpatient		Emergency		Both settings		First occurrence		Recurrence	
	Frequency n (%)	Rate (95% CI)*	Frequency n (%)	Rate (95% CI)*	Frequency n (%)	Rate (95% CI)*	Frequency n (%)	Rate (95% CI)*	Frequency n (%)	Rate (95% CI)*	Frequency n (%)	Rate (95% CI)*	Frequency n (%)	Rate (95% CI)*	Frequency n (%)	Rate (95% CI)*	Frequency n (%)	Rate (95% CI)*	Frequency n (%)	Rate (95% CI)*
Specific diagnoses																				
diagnosis 1																				
diagnosis 2																				
Diagnosis groupings																				
grouping 1																				
grouping 2																				
etc.																				

*Events per 1000 person years

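### SAP 5.2 and the SAP section 8 footnote give different denominators for the single-diagnosis rates in Table 5b, and the code-based exclusion behind those rates has an undisclosed gap: no test of resolution

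*SAP*

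**What the plan says.** **Numerator.** SAP 5.1 has a diagnosis "excluded as pre-existing if the same ICD diagnosis code appears in any medical setting prior to the first dose". There is no look-back limit and no question about resolution. Table shell 4b applies this as an automated step, column (b), before physician review. The count carried forward is i = a − b − e − f − g, so nothing in (b) returns. After dose 1 the treatment differs: "The analysis allows for any recurrent events (i.e. different episodes of the same diagnosis) to be counted independently", with the end of an episode judged by chart review. At the encounter level the rule is softer: "Encounters will be considered pre-existing if all diagnoses made during the encounter are present in the medical record prior to the first dose of vaccine".

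**Denominator.** Protocol 9.7.3 defines the rate as "the number of all captured events divided by the total person-time following MenACWY-CRM doses administered during the study period". SAP 5.2 repeats this: captured events are "divided by the total person-time following MenACWY-CRM doses administered during the study period". It then sets out when person-time starts and stops for each dose, without removing anyone with an earlier code.

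**Population.** SAP section 8 lists Tables 4, 5 and 6 as per-event tables, and the footnote explains: "Per event will include all recipients with no history of that event prior to the first MenACWY-CRM dose". The Table 5b shell gives the unit (per 1000 person-years) but no denominator.

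**Disclosure.** SAP 5.4 plans no sensitivity analysis. On pre-existing conditions, SAP 6.2 mentions only that some may escape the automated search because ICD-9 and ICD-10 do not map perfectly.

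**The concern.** Describing emergency and inpatient events after vaccination is the study's only objective, and Table 5 is the only place where event rates appear. Two programmers could each follow the SAP faithfully and report different single-diagnosis rates. One works from 5.2 and keeps all person-time. The other works from the section 8 footnote and drops children with a history. The first rate combines a restricted numerator with an unrestricted denominator, and in a safety report that error runs downwards.

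The footnote does not settle the matter as it stands. Applied literally to Table 4b, it would leave column (b) empty. It has no defined meaning for the encounter rows of Table 5a, where an encounter counts as pre-existing only if all its diagnoses do. Nor does it say whether history for a diagnosis grouping means the same code or any code in the group.

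Separately, two identical new episodes after vaccination are handled differently according to when the earlier, resolved episode was coded. If it was coded after dose 1, the new episode counts as a recurrence. If it was coded before dose 1, the new episode is dropped. For example, a child with code 282.62 (an indication code in SAP Appendix B) on record before dose 1 can have no later crisis under that code counted in Table 5b. This shows the mechanism, not its size.

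**Working it through.** **Inputs.** From SAP 3.2: N = 100, one person-year each (T = 100), and a rate of 10 per 100 person-years, used here as r0, the rate in children without the earlier code. Assumed, because the documents give neither: p, the share of person-time from children with the earlier code (10%, 30%, 50%), and s, the share of column (b) events that are truly new episodes (0 to 100%).

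**Step 1: the plan's own figures.** Exact Poisson limits are χ²(0.025; 2x)/2 ÷ T and χ²(0.975; 2x+2)/2 ÷ T. For x = 10 and T = 100 they give 4.8–18.4, as printed in SAP 3.2. Ten of the twelve cells match to one decimal. The other two differ by 0.1 (9.348 is printed as 9.4, and 3.247 as 3.3). Nothing below depends on those two cells.

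**Step 2: denominator.** No event under the code is counted in children who already had it, so the count is x = r0 × (1 − p) × T.

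- Under 5.2 read literally: x / T = (1 − p) × r0.
- Under the section 8 footnote: x / [(1 − p) × T] = r0.
- The ratio is 1 − p. It needs no assumption about the event rate in children with the code.

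| p | Events counted | 5.2: per 100 PY (95% CI) | Footnote: per 100 PY (95% CI) |
|---|---|---|---|
| 10% | 9 | 9/100 = 9.0 (4.1–17.1) | 9/90 = 10.0 (4.6–19.0) |
| 30% | 7 | 7/100 = 7.0 (2.8–14.4) | 7/70 = 10.0 (4.0–20.6) |
| 50% | 5 | 5/100 = 5.0 (1.6–11.7) | 5/50 = 10.0 (3.2–23.3) |

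**Step 3: numerator.** Assume children with the code have the same event rate. Then r0 × p × T = 1, 3 or 5 of 10 expected post-dose events fall into column (b). Only the share s of these are new episodes. Restoring them over the same total person-time multiplies the rate by 1 + p × s / (1 − p):

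| p | s = 0 | s = 25% | s = 50% | s = 100% |
|---|---|---|---|---|
| 10% | 1.00 | 1.03 | 1.06 | 1.11 |
| 30% | 1.00 | 1.11 | 1.21 | 1.43 |
| 50% | 1.00 | 1.25 | 1.50 | 2.00 |

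**Step 4: a trap in any sensitivity analysis.** At p = 30% and s = 50%, the restored rate over total person-time is (7 + 1.5)/100 = 8.5. Against an at-risk main rate of 7/70 = 10.0, restoring events would appear to lower the rate. Against 7/100 = 7.0 the factor is 8.5/7.0 = 1.21, which is the effect of interest. The two rates must share a denominator.

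**The case against.** A reader might infer that Table 5b rates are in fact diluted. The documents do not support that. The footnote can be applied literally to single-diagnosis rows, and doing so removes the dilution entirely, leaving the rate in children at risk of a first coded diagnosis. Nor does the opening of SAP section 5, "The outcome data will be provided for the entire population", settle the question the other way: there the whole population is contrasted with strata by number of doses, and no rate denominator is being defined. This objection stands, and it limits the point to an unreconciled instruction.

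A reader might also infer that many events are lost. That is not supported either. If s is near zero, the exclusion costs almost nothing. No basis is given for p as high as 50% on a single code, and a child who starts at 2 months of age has only about two months of earlier record. The paired intervals in the working overlap heavily. Column (b) does show how many diagnoses were excluded, though it does not separate ongoing conditions from new episodes.

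Finally, the exclusion rule is prespecified and stated consistently in both documents, the study is descriptive with 60–100 high-risk children expected, and chart review to restore events would add retrospective judgement by reviewers who know vaccination status. That is a fair reason not to require such a review. It does not excuse leaving the denominator unstated or the missing resolution test undisclosed.

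**Conclusion.** The point holds as an inconsistency that should be fixed. SAP 5.2 (with Protocol 9.7.3) and the section 8 footnote prescribe different denominators for the study's only event rates, and the footnote cannot be applied as written to Table 4 or Table 5a. If 5.2 is followed, single-diagnosis rates in Table 5b fall by the fraction p, which is 10–50% over the assumed range. If the footnote is followed, they do not fall at all.

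Under both readings, new post-dose episodes of a condition that resolved before dose 1 are left out, and SAP 6.2 does not list this among the limitations. The size of that loss cannot be fixed from the documents, because it depends on p, on s and on the event rate in children with the code.

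Confidence is high for the inconsistency and for the missing resolution test, and moderate for the denominator effect, which depends on which instruction the programmer follows. No hypothesis test is affected.

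**What to change.** 1. **Denominator.** Amend SAP 5.2 so that single-diagnosis rows of Table 5b, in every column, use the person-time of recipients without that code before dose 1, in line with the footnote. Keep total person-time for Table 5a. For grouping rows, define history at one level (code or group) and use it in both numerator and denominator. Reword the footnote so that it does not cover Table 4 or Table 5a.
2. **Limitation.** State in SAP 6.2 that the code exclusion does not test for resolution, so the rates omit new episodes of conditions resolved before dose 1. Point the reader to Table 4b column (b) for the number excluded.
3. **Optional sensitivity analysis.** Have the same physician review column (b) events, restore the new episodes using the existing SAP 5.1 episode rule, and compare the result with the prespecified numerator over the same total person-time, so that only the numerator changes.
4. **Review scope.** SAP 3.1 sends all identified events to physician review, whereas Protocol 9.4.2 (step 5) limits chart review to eligible ones. Say which applies.

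**Cost.** Items 1, 2 and 4 are a few lines of text plus a person-time calculation for each code. Item 3 adds one re-run of the tables and some chart reviews. Their number is the column (b) count, which is not in the documents but is known from the automated step before review starts.

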5.2 Frequency and rate of events

The frequency of medical events is defined as the total number of each individual event. The frequency will be described by absolute number of each individual medical event and percentage of each individual medical event out of the total number of captured medical events during the observation period and included for analysis (as per Tables 4a or 4b).

The rate of medical events is defined as the number of all captured events divided by the total person-time following MenACWY-CRM doses administered during the study period. The rate and Poisson 95% confidence interval of the rate of medical events will be calculated and presented as number per 1000 person-years using SAS PROC GENMOD.

If the number of medical events allows, captured medical events will be stratified by dose and by the status of the diagnosis as first occurrence or recurrence. Person-time for each dose will begin at the date of vaccination and end at 6 months following vaccination, disenrollment, death, the end of data collection, or receipt of an additional dose of MenACWY-CRM, whichever comes first.

Frequency and rate of events will be characterized two ways: by encounter (hospitalization only, ED only, or both ED and hospitalization) and by diagnosis (see Appendix A, Table Shell 5 for details). For the analysis by encounter, the encounter date will be used to determine the timing of the encounter relative to the timing of vaccine dose. For the analysis by diagnosis, the first diagnosis date for each diagnosis in any care setting will be used to determine the timing of the diagnosis relative to the timing of vaccine dose. The analysis by diagnosis will be stratified by setting of diagnosis and recurrence when the number of events in each stratum is ≥ 5 . The setting of diagnosis reflects whether the diagnosis was captured by automated search in the inpatient setting, ED setting, or both. If possible, diagnoses will be grouped by category, and the frequency and rate of diagnoses will be presented by category.

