Plan Prepared by: PPD, MS
Research Manager, Biostatistics
Kaiser Permanente Southern California

Version and Date: Version 2.0: 17 November 2015

Approvals

Approvers, Organization & Role	Approval Status	Date
PPD [REDACTED], MS KPSC Research and Evaluation Research Manager, Biostatistics	Approved	11/17/2015
PPD [REDACTED] KPSC Research and Evaluation Principal Investigator	Approved	11/17/2015
PPD [REDACTED] Department of Epidemiology GlaxoSmithKline Epidemiologist	Approved	11/17/2015

Publication Record

Version	Date	Primary Author	Description
1.0	September 18, 2015	PPD [REDACTED]	1 st Draft for GSK Review
1.1	October 16, 2015	PPD [REDACTED]	2 nd Draft for GSK Review
1.2	October 30, 2015	PPD [REDACTED]	Final draft for GSK Review
1.3	November 6, 2015	PPD [REDACTED] [REDACTED]	Comments on Draft 1.2
1.4	November 11, 2015	PPD [REDACTED]	Final draft for GSK Review
2.0	November 17, 2015	PPD [REDACTED]	Approvals obtained, SAP finalized

Definitions

Concomitant vaccination(s) – any other vaccination(s) administered to a subject on the same date as a MenACWY-CRM vaccination.

Day 0 - For the calculation of study day, Day 0 is the date when the index vaccination is received.

Event – Events are classified on an encounter level and a diagnosis level. For encounters, an inpatient admission, emergency department (ED) visit, or an ED visit resulting in an inpatient admission will each be treated as a single event. For diagnoses, all medical diagnoses made during ED and inpatient visits are considered events, which will be further classified as pre-existing, new, recurrent, or part of an ongoing episode.

Episode – Diagnosis-type medical events that result in multiple encounters during the observation period are considered episodes. Episodes comprise the course of a disease or condition, from initial presentation through resolution, as determined through chart review. An episode will be consolidated as a single event for analysis. For each episode, the first diagnosis date in any care setting will be used for analyses.

First-dose - no prior dose of a quadrivalent meningococcal conjugate vaccine recorded in the full medical history

Index vaccination – The first receipt of MenACWY-CRM at a KPSC facility between July 1, 2014 and June 30, 2017 in a study subject of which the date of administration defines the start of the observation period.

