3. STUDY DESIGN

3.1 Overview of study design

This study is a descriptive observational study expected to span multiple years. This study will include members of Kaiser Permanente Southern California (KPSC) HMO vaccinated with MenACWY-CRM as part of their routine clinical care. Patients will be between the ages of 2 and 23 months.

The vaccination period spans three years, with the number of study subjects determined by the number of KPSC members aged 2-23 months who receive their index MenACWY-CRM vaccination between July 1, 2014 and June 30, 2017. The observation period for each recipient is defined as the time from the first dose of MenACWY-CRM vaccination up to 6 months after the last dose of MenACWY-CRM vaccination received between 2-23 months of age, disenrollment, death, or the end of data collection (November 30, 2017), whichever occurs sooner. Vaccination status is obtained from the information in the vaccination records of the electronic medical record (EMR).

Medical events in ED and inpatient care units in children 2-23 months of age who were vaccinated with any dose of MenACWY-CRM vaccine will be described. Medical events that occur up to six months following a dose of MenACWY-CRM, receipt of a subsequent MenACWY-CRM vaccination, disenrollment, death, or the end of data collection, whichever occurs sooner will be captured. Events will be identified from EMRs of ED and inpatient care encounters. Events with a history of the same diagnosis prior to the first dose of MenACWY-CRM vaccination will be excluded as a pre-existing condition. Medical records of these events will be reviewed and described.

All events occurring during the observation period are assessed retrospectively. One subject can experience multiple different events. All identified events will be reviewed by a general physician (study co-investigator) to determine the final diagnosis/diagnoses for the encounter.

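### SAP 5.2 gives all-event rates a Poisson interval that assumes independent events, which is too narrow for frequent rows if children differ in their event rates

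*SAP*

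**What the plan says.** The rate in SAP v2.0 section 5.2 is all captured events over total person-time. Its uncertainty is given in one phrase: "Poisson 95% confidence interval of the rate of medical events will be calculated and presented as number per 1000 person-years using SAS PROC GENMOD". Neither the SAP nor protocol 9.7.3 mentions a dispersion parameter, a REPEATED statement, a robust variance or a negative binomial model. SAP 5.4 plans no sensitivity analyses.

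The counting rules let one child contribute more than once. SAP 3.1 says "One subject can experience multiple different events", and 5.1 says "The analysis allows for any recurrent events (i.e. different episodes of the same diagnosis) to be counted independently". SAP 5.2 also pools diagnoses: "If possible, diagnoses will be grouped by category, and the frequency and rate of diagnoses will be presented by category".

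Other rules remove duplicates. Under the definition of an episode, "An episode will be consolidated as a single event for analysis". An ED visit leading to admission is one event. In the encounter analysis, "Each encounter will be reported as a single event, regardless of the number of diagnoses made during the encounter". Conditions already coded before the first dose are excluded.

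Table shells 4a and 4b have rows for "Number of recipients experiencing multiple different hospitalization or emergency encounters" and "Number of recipients experiencing multiple different diagnoses". These are summary rows; Tables 5a and 5b have no such count for each event row or dose column.

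**The concern.** A Poisson interval sets the variance of the total count equal to its mean. That fails when some children have persistently higher event rates than others, because their repeat visits add variance. Such differences are plausible here. Protocol 9.2.2 expects vaccinees with sickle cell disease, asplenia or complement deficiency alongside children vaccinated for travel or an outbreak.

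Merging episodes and ED-to-ward transfers removes duplicate records of one illness. It does not remove dependence between separate illnesses or visits in the same child.

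The study has no comparator and no hypothesis test, so the rates and their intervals are its main quantitative statement. The planned interval would be identical whether each event came from a different child or many came from a few, and a Table 5a or 5b row would not show which.

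**Working it through.** **Inputs.** SAP 3.2 gives a mean follow-up of 1 PY per child and planning rates of 0.1, 1, 10 and 100 per 100 PY. It also expects 60-100 high-risk infants. That is not a forecast of vaccinees (protocol 9.5 plans no number), so N = 60-100 is illustrative. Under SAP 5.2, person-time for a dose ends at six months or the next dose, so a child gives a dose column at most 0.5 PY. Dispersion is not given; CVs of 0, 0.55, 1.0 and 1.41 are assumed and held fixed across rates.

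**The plan's own table.** With D = rate × N × 1 PY, exact Poisson limits are χ²(0.025; 2D)/2 and χ²(0.975; 2D+2)/2, divided by person-years. At 100 per 100 PY this gives 74.2-131.8, 81.4-121.6 and 84.6-117.3 for N = 50, 100 and 150, as printed. Ten of the 12 cells match. The other two differ by rounding (9.348 printed as 9.4, 3.247 as 3.3). The planned precision therefore assumes independent events.

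**Effect of child differences.** If child rates follow a gamma distribution, the variance/mean ratio of counts per child is φ = 1 + rate × PY × CV². Large-sample coverage of the Poisson interval is then about 2Φ(1.96/√φ) − 1. Simulated coverage uses gamma-Poisson counts, N = 60 and 100, and log-scale limits r·exp(±1.96/√D), D now being the observed count:

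| Setting | φ at CV 0, 0.55, 1.0, 1.41 | Simulated coverage in that order |
|---|---|---|
| 1 per PY, 1 PY each | 1, 1.3, 2, 3 | 95-96%, 91-92%, 83-85%, 74-76% |
| 0.3 per PY, 1 PY each | 1, 1.09, 1.3, 1.6 | 95-96%, 94-95%, 91-92%, 87-89% |
| 0.1 per PY, 1 PY each | 1, 1.03, 1.1, 1.2 | 94-96% throughout |
| 1 per PY, dose column, 0.5 PY each | 1, 1.15, 1.5, 2 | about 95%, 93%, 88-89%, 82-83% |

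As a check, φ = 2 gives 2Φ(1.96/1.414) − 1 = 83.4%, and φ = 3 gives 74.2%. SAP 5.2 does not say which limits GENMOD will report, but the choice matters little here. At φ = 2 and 1 PY each, exact limits cover 86.0% (N=60) and 84.1% (N=100).

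**Robust limits.** Take the standard error of the log rate as √Σ(yᵢ − r·tᵢ)² / Σyᵢ, where yᵢ and tᵢ are each child's events and person-time. Coverage at 1 per PY and 1 PY each is then about 93-95% across all four CVs.

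**Size on a reported rate.** Take 20 events in 100 children and 100 PY, a rate of 200 per 1000 PY. The limits are 200·exp(±1.96·√(φ/20)):
- Planned, φ = 1: 129-310.
- CV 1.0, φ = 1 + 0.2 × 1 = 1.2: 124-323.
- CV 1.41, φ = 1 + 0.2 × 2 = 1.4: 119-336.

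**The case against.** **Scope is narrow.** Three of the four planning rates in SAP 3.2 lie at or below 10 per 100 PY, where there is no material loss. Table 5a has no all-encounter total, only three mutually exclusive rows, so a single category would have to approach 1 event per child-year for the largest losses. No document forecasts such a rate. This stands and limits the point. It does not remove it: 100 per 100 PY is one of the SAP's own planning rows, and groupings pool diagnoses, several of which can come from one visit.

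**The study is descriptive and multiple-event children are already tabulated.** The rates themselves are unaffected, and Tables 4a and 4b disclose some of the clustering. Both are true, but neither widens an interval labelled 95% nor shows the clustering behind a particular row.

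**Dose columns.** With at most 0.5 PY per child, excess variance there is half or less of the full-year value. This stands, and the dose-column figures above allow for it.

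**A stronger reading to avoid.** A reader might infer that a handful of children could make the planned interval grossly wrong. If 20 events came from ten children with two each, the robust interval would be 111-360. If they came from four with five each, it would be 77-522. Those patterns have variance/mean ratios of (40/100 − 0.04)/0.2 = 1.8 and (100/100 − 0.04)/0.2 = 4.8. Solving φ = 1 + 0.2 × CV² gives CVs of about 2 and 4.4, beyond the assumed maximum of 1.41. They illustrate extreme clustering, and nothing in the documents suggests it is expected.

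**Conclusion.** The concern holds for frequent all-event rates. SAP 5.2 specifies a Poisson interval with no allowance for several events in one child. At 1 event per PY overall, coverage could fall from 95% to about 91-92% with modest differences between children, or to 74-76% with strong ones. At 0.3 per PY the loss is smaller, and at 0.1 per PY it is immaterial. These sizes rest on assumed gamma-distributed child rates, the assumed CV range and 60-100 vaccinees; if children do not differ, there is no loss.

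The documents do not support reading this as a defect in every interval. First occurrences of a single diagnosis contribute at most one event per child, and rare events are barely affected. Nor is it a bias in the rates. The change is worth making before analysis because the intervals carry the study's statement of uncertainty.

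**What to change.** In SAP 5.2:
- Keep the Poisson point estimate. For frequent all-event rates, use child-level robust limits: PROC GENMOD with REPEATED SUBJECT=child, an independence working correlation and a log person-time offset.
- For zero or sparse counts and small strata, use exact Poisson limits, labelled as assuming independent events. This also settles which limits are reported; if 5.2 means log-scale Wald limits, a zero-event row would have no interval.
- State the switch point before the data are seen. The SAP's n ≥ 5 thresholds govern what is presented and do not by themselves justify a robust variance.
- Show the number of distinct children with an event beside each count in Tables 5a and 5b, with the small-cell suppression used for Tables 2 and 3 if needed.
- Label the 3.2 table as assuming independent events.

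The cost is some SAP wording, one REPEATED statement, an exact-limit step and one column; no new data are needed. Intervals become wider when children differ, by about 38% at CV 1.0 and 1 event per PY.

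Robust limits still under-cover somewhat with very few children, and exact limits do not fully protect small strata. With ten children at 0.5 PY each and 1 event per PY, exact limits cover about 98%, 97%, 94-95% and 91% across the four CVs. The independence label and the count of children are therefore needed there.
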